#### 3.2 Secondary Objectives

The secondary study objectives are the following:

- Feasibility: Evaluate the feasibility of the Empower Neuromodulation System treatment via its ability to provide effective nerve stimulation (via participant-reported tingling sensation, a direct indication of effective nerve stimulation)
- Acceptability: Evaluate the acceptability of the Empower Neuromodulation System treatment via overall satisfaction with treatment (via 100-mm VAS)
- Safety: Evaluate the safety of the Empower Neuromodulation System treatment via device-related adverse events
- Effectiveness: Evaluate the effectiveness of the Empower Neuromodulation System treatment for (all endpoints assessed for active vs. sham groups):
  - Reducing clinician-assessed anxiety severity (via Hamilton Anxiety Rating Scale (HAM-A))
  - Reducing participant-reported anxiety severity (via Beck Anxiety Inventory (BAI), Generalized Anxiety Disorder Questionnaire-IV (GAD-Q-IV), daily self-reports for anxiety severity (100-mm VAS), and pre- and post-treatment self-reports of anxiety severity (100-mm VAS))
  - Reducing participant-reported anxiety interference with daily living (via daily self-reports for anxiety interference with daily living (via 100-mm VAS))
  - Reducing medication use (via self-reports)
  - Reducing clinician-assessed depression severity (via Hamilton Depression Rating Scale (HAM-D))
  - Reducing participant-reported depression severity (via Patient Health Questionnaire-9 (PHQ-9))
  - Reducing participant-reported post-traumatic stress disorder (PTSD) severity (via PTSD Checklist-5 (PCL-5))
  - Improving sleep quality (via Pittsburg Sleep Quality Index (PSQI) survey)
  - Improving quality of life (via SF-12 survey)
- Blinding: Evaluate if the active and sham treatments are well-blinded per the blinding assessment

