### 5.2 Secondary Endpoints

The following secondary endpoints will be evaluated:

- Feasibility: For each treatment group, the percentage of treatment sessions that provide effective nerve stimulation as assessed via participant-reported confirmation of tingling sensation
- Acceptability: For each treatment group, the overall satisfaction with treatment (via 100-mm VAS)
- Effectiveness:
  - Effect of treatment group on change in clinician-assessed anxiety severity (via HAM-A)
  - Effect of treatment group on change in weekly participant-reported anxiety severity (via BAI)
  - Effect of treatment group on change in participant-reported GAD symptoms (via GAD-Q-IV)
  - Effect of treatment group on change in daily self-reports for anxiety severity (via 100-mm VAS)
  - Effect of treatment group on change in self-reports of anxiety severity immediately after vs. before treatment (via 100-mm VAS)
  - Effect of treatment group on change in daily self-reports for anxiety interference with daily living (via 100-mm VAS)
  - Effect of treatment group on medication use (via self-reports)
  - Effect of treatment group on change in clinician-assessed depression severity (via HAM-D)
  - Effect of treatment group on change in participant-reported depression severity (via PHQ-9)
  - Effect of treatment group on change in participant-reported PTSD severity (via PCL-5)
  - Effect of treatment group on change in sleep quality (via PSQI survey)

- Effect of treatment group on change in quality of life (via SF-12 survey)
- Blinding: For each treatment group, the blinding index and 95% confidence interval (via Bang et al. blinding assessment method)

All of these secondary endpoints provide valuable information on the effectiveness of the Empower Neuromodulation System for GAD treatment as well as the acceptability to the intended patient population.

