### 6.3 Exclusion Criteria

1. Has current (past 30 days) psychotic or bipolar disorder, homicidal ideation, psychiatric hospitalization, or moderate/severe SUDs per clinician assessment via M.I.N.I.
2. HAM-D  $\geq 18$
3. PCL-5  $\geq 34$
4. Exhibits suicidal intent as confirmed on the Columbia-Suicide Severity Rating Scale-Revised (C-SSRS-R) with a “Yes” response to question 4 or question 5, or to question 6 in the past 3 months.
5. Changes in psychoactive medications in the past 30 days (including but not limited to psychotropic medications, thyroid hormone medication, steroids), with the exception of benzodiazepines
6. If regularly taking benzodiazepines, has had changes in benzodiazepine dosing in the past 30 days or average use  $> 2$  days per week
7. Psychotherapy was initiated or discontinued in the past 30 days or psychotherapy modality was changes in the past 30 days
8. Has a history of epilepsy or a seizure disorder

9. Has been diagnosed with peripheral nerve damage of the arm or hand or has numbness or tingling in the arm or hand at least weekly
10. Is currently pregnant or breastfeeding, has been pregnant within the past 6 months or intends to become pregnant during the study period
11. Currently has an active implant and/or an electrical or neurostimulator device, including but not limited to cardiac pacemaker or defibrillator, vagal neurostimulator, deep brain stimulator, spinal stimulator, sacral stimulator, bone growth stimulator, or cochlear implant
12. Has an electrically conductive metal object (e.g. jewelry) that cannot be removed from [REDACTED] and will directly contact the gel electrodes of the Empower Neuromodulation System at either anatomic location
13. Has an open incision, wound, scar, active infection or otherwise compromised skin at the [REDACTED] and will directly contact the gel electrodes of the Empower Neuromodulation System at either anatomic location
14. Does not have daily access to an electrical outlet for charging the investigational device and associated smartphone
15. Has used of an investigational drug/device therapy within the past four weeks
16. Unable to provide informed written consent
17. Has any medical condition that would, in the opinion of the investigator, make the participant ineligible

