### **9.1 Clinical Assessments**

#### **9.1.1 Concomitant Medications**

All concomitant medication and concurrent therapies will be documented at Screening. Dose, route, unit frequency of administration, and indication for administration and dates of medication will be captured.

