#### 15.4 Analysis of Secondary Endpoints

Secondary endpoints will be analyzed via the methods described below. Unless otherwise noted, for daily and weekly metrics, we will use a random-intercept linear mixed model with restricted maximum likelihood to compare results between the active and sham treatment groups. As a secondary analysis for each of these endpoints, we will evaluate the correlations for duration since last benzodiazepine dose and dose amount vs. the endpoint. If this relationship is significant for an endpoint, we will include time since last dose in our statistical analysis.

Feasibility: Effective nerve stimulation: We will calculate effective nerve stimulation (treatment sessions that elicit skin tingling as a percentage of total treatment sessions) for each participant. We will also compare effective nerve stimulation between the active and sham treatment groups (t-test).

Acceptability: Overall satisfaction with treatment: We will compare overall satisfaction with treatment scores between the active and sham treatment groups (t-test).

Safety: We will tabulate AEs across all participants. This will include tabulating the number of participants for whom the event occurred, the rate of occurrence, and the severity and relationship to the study device.

Effectiveness: Change in HAM-A score: We will compare the change in HAM-A score between the active and sham treatment groups (t-test).

Effectiveness: Change in GAD-Q-IV score: We will compare the change in GAD-Q-IV score between the active and sham treatment groups (t-test).

Effectiveness: Change in BAI score: We will compare the change in BAI score between the active and sham treatment groups (mixed models).

Effectiveness: Change in daily anxiety severity self-report: We will compare the change in daily anxiety severity scores between the active and sham treatment groups (mixed models).

Effectiveness: Change in daily anxiety interference self-report: We will compare the change in daily anxiety interference scores between the active and sham treatment groups (mixed models).

Effectiveness: Change in anxiety severity self-report as an immediate result of treatment: We will compare the short-term effect of Empower treatment on anxiety severity score (% change for post-treatment score vs. pre-treatment score) (repeated measures ANOVA with Tukey correction, active vs. sham treatment group).

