Effectiveness: Medication use: We will calculate average benzodiazepine use per week. We will compare medication use between the active and sham treatment groups (mixed models).

Effectiveness: Change in HAM-D score: We will compare the change in HAM-D score between the active and sham treatment groups (t-test).

Effectiveness: Change in PHQ-9 score: We will compare the change in PHQ-9 score between the active and sham treatment groups (t-test).

Effectiveness: Change in PCL-5 score: We will compare the change in PCL-5 score between the active and sham treatment groups (t-test).

Effectiveness: Change in PSQI score: We will compare the change in PSQI score between the active and sham treatment groups (t-test).

Effectiveness: Change in SF-12 score: We will compare the change in SF-12 score between the active and sham treatment groups (t-test).

Blinding: We will statistically assess blinding for the active and sham treatment groups using the blinding index from Bang et al.

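### Benzodiazepine use is compared between arms without adjusting for pre-treatment use, although reduction is the objective and a baseline is already recorded at Screening

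*Combined protocol and SAP*

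**What the plan says.** Section 3.2 lists "Reducing medication use (via self-reports") among the effectiveness objectives, all of which are to be assessed as active versus sham. Section 5.2 names the endpoint as "Effect of treatment group on medication use (via self-reports"). It is one of twelve effectiveness endpoints there, and the other eleven are worded as a change.

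Section 15.4 says "We will calculate average benzodiazepine use per week" and then "We will compare medication use between the active and sham treatment groups (mixed models"). It does not say whether use is counted in days, doses or amount. The general rule for daily and weekly measures is that "we will use a random-intercept linear mixed model with restricted maximum likelihood to compare results between the active and sham treatment groups"; the fixed effects are not listed. Apart from group, the only term that the section provides for is time since the last benzodiazepine dose, and that is conditional: "If this relationship is significant for an endpoint, we will include time since last dose in our statistical analysis".

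Three other parts of the protocol bear on this:

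- **Who can be a user.** Exclusion 6 in Section 6.3 reads "If regularly taking benzodiazepines, has had changes in benzodiazepine dosing in the past 30 days or average use" above 2 days per week. Section 7.1 permits benzodiazepines but does not require them, so users and non-users both enter. Section 7 asks that psychoactive medication be kept the same during the study where medically feasible.
- **Allocation.** Sections 8.1 and 15.5 describe 1:1 randomisation with men and women randomised separately, and Section 15.5 plans 15 per arm. Part of the text is redacted. Sex is the only stratification factor visible.
- **Data.** For Screening, Section 9.1.1 states: "Dose, route, unit frequency of administration, and indication for administration and dates of medication will be captured". Under Section 9.1.7.1 the app asks daily, before the first session, about non-scheduled anxiety medication over the previous 24 hours.

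**The concern.** Most non-users can be expected to stay at or near zero, and regular users enter within a narrow capped range. In-study weekly use will therefore depend heavily on who was a user at entry and how much they took. Allocation of 30 people with no visible stratification on this factor leaves the split of users to chance. The planned analysis leaves that variation in the arm difference, although the data that would remove much of it are already collected.

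At stake is how the result can be read. A real reduction could be hidden or appear with the wrong sign because the active arm drew a few more users. An apparent reduction could largely reflect the opposite draw. The existing covariate rule does not help, because time since last dose is measured during the study and is not pre-treatment use.

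**Working it through.** **1. The plan's own figure.** The plan gives no power, effect size or standard deviation (SD) for this endpoint. The sample size is set by precedent: 2 × 15 = 30, which agrees with 60 × (1 − 0.5) = 30. There is nothing further to reproduce.

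**2. What the planned comparison estimates.** Let Y be in-study use and B pre-treatment use. Under randomisation E(B_active) = E(B_sham), so E(Y_active − Y_sham) = E[(Y_active − B_active) − (Y_sham − B_sham)]. The arm difference in level therefore has the same expectation as the arm difference in change. Baseline affects the variance and not the target.

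**3. How uneven the split of users can be.** With K users among 30, split 15/15 and ignoring sex strata, P(a users in active) = C(15,a)·C(15,K−a)/C(30,K). For K = 9 the arms differ by only 1 when a = 4 or 5. Each of these has probability 1365 × 3003 / 14,307,150 = 0.2865, so P(difference of 3 or more) = 1 − 2 × 0.2865 = 0.43. The probability that the arms differ by 2 or more users is 22% for K = 3, 65% for 6, 43% for 9, 71% for 12 and 47% for 15. (The difference is even when K is even and odd when K is odd, so these values do not move smoothly.)

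**4. What that does to the estimate.** The assumptions, none of them in the documents, are:

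- outcome in days per week;
- habitual use uniform on 0.25 to 2 days per week among users (mean 1.125) and zero among non-users;
- within-person drift with log-SD 0.3;
- 42 days of follow-up;
- baseline from a 28-day recall, so measured with error;
- complete data, in which case the group effect in a random-intercept model equals a t-test on participant means.

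With 9 users, a 50% reduction is worth 0.5 × 9/30 × 1.125 = 0.169 days per week. Three extra users in one arm are worth 3 × 1.125/15 = 0.225 days per week, which is more than that effect.

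Under no treatment effect, the user count alone accounts for 68% of the variance of the arm difference with 3 users, 66% with 6, about 62% with 9, 59% with 12 and 54% with 15. It falls to 44% with 20, 29% with 25 and 0% with 30.

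**5. Effect of adjusting for baseline (ANCOVA).** SDs are for the arm difference under no effect. The variance ratio is (SD unadjusted / SD adjusted)². Power and wrong-sign columns are for a true 50% reduction, unadjusted to adjusted.

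| Users of 30 | SD unadjusted | SD adjusted | Variance ratio | Power | Wrong-sign estimate |
|---|---|---|---|---|---|
| 3 | 0.152 | 0.066 | 5.3 | near 0 in both | 31% to 29% |
| 6 | 0.204 | 0.105 | 3.8 | 5% to 7% | 23% to 14% |
| 9 | 0.241 | 0.133 | 3.3 | 8% to 18% | 18% to 8% |
| 12 | 0.263 | 0.157 | 2.8 | 13% to 29% | 15% to 5% |
| 15 | 0.285 | 0.180 | 2.5 | 19% to 39% | 9% to 3% |

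**6. Error rate.** Under no effect the unadjusted comparison rejects in 4% to 5% of runs with 6 or more users, and almost never with 3.

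**7. Sensitivity to the quality of the baseline.** If baseline is taken as known exactly (users at 0.5 to 2 days per week, in-study use equal to baseline plus noise of SD 0.5), the SDs are 0.212 and 0.077 at 20% users, 0.240 and 0.096 at 30%, and 0.286 and 0.128 at 50%. The variance ratios are then 7.6, 6.3 and 5.0. The Screening record will not be that accurate, so the table in step 5 is the better guide.

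**The case against.** The strongest defence is that the comparison is valid as written. Step 2 shows that it estimates a treatment-caused reduction, and the uncertainty from an uneven split of users is carried in the standard error. This stands. A reader might infer that the analysis is biased, or that it cannot address the objective; neither follows.

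It can also be said that the number of users is unknown, so no statement about what drives the result is certain. This stands too, and it makes the concern conditional.

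Three points of text soften the criticism without removing it. The fixed effects are not listed, so a group-by-week term may be intended; that would track change during treatment but would not use pre-treatment use. Section 15.2 summarises the primary antianxiety medication at screening, but it does not say by arm and does not cover amount or frequency of benzodiazepine use. The first app report on Day 1 precedes treatment, but one 24-hour window says little about someone who takes the drug on at most 2 days a week.

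Finally, adjustment leaves power low, and this is one of twelve secondary effectiveness endpoints in a pilot whose co-primary endpoints are adherence and usability. Both points are correct and limit the weight of the finding.

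**Conclusion.** The concern holds as one of precision and interpretation. The analysis of medication use leaves out pre-treatment use, although the objective is reduction, the companion endpoints use change, and the baseline is already collected. If users are a minority, chance imbalance in baseline use can largely drive the estimate. The 2.5- to 5-fold variance gain from adjustment rests on 3 to 15 users and the assumptions in step 4.

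Four stronger readings are not supported:

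- That imbalance is bound to dominate: this depends on a user count that the documents do not give, and the share due to user count vanishes if everyone is a user.
- That false positives rise: they do not.
- That no baseline exists: it is missing from the analysis, not from data collection.
- That allocation is stratified by sex alone: redaction means that sex is only the sole factor visible.

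No primary conclusion is affected.

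**What to change.** In Section 15.4:

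1. State the unit of weekly benzodiazepine use.
2. Derive pre-treatment use in that same unit from the Screening medication record, and include it as a pre-specified covariate in the mixed model, whether or not it is significant.
3. Report the number of baseline users in each arm.
4. Present change among baseline users as a description only. It subtracts a Screening record from an app diary, and may cover few people: about 9 across both arms if 30% are users.

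The cost is one covariate and one short table, with no new visit or instrument. Exclusion 6 already requires the site to establish average days of use per week in regular users. The drawback is that baseline and outcome come from different instruments. This reduces the gain in precision but does not bias the adjusted arm comparison, because the baseline is recorded before randomisation.

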## 15.5 Randomization and Sample Size

At enrollment, participants will be randomized (1:1, [REDACTED] stratified by sex) to the active or sham stimulation. Participants will also be randomized for the body side that they should apply stimulation to first (right vs. left, 1:1 simple randomization). Men and women will be randomized separately.

As a pilot study, our primary goal is to demonstrate feasibility for GAD treatment. Accordingly, the study sample size is based on similar pilot GAD studies in the literature. For two rTMS studies, each treatment arm had 12-25 participants, with an average of 15 participants. To be consistent with these studies, we will enroll 15 participants per treatment arm, for a total of 30 participants.

## 16 DATA COLLECTION, RETENTION AND MONITORING

### 16.1 Data Collection Instruments

Study personnel will enter data from source documents corresponding to a participant's visit into the protocol-specific electronic Case Report Form (eCRF) OR paper CRF when the information corresponding to that visit is available. Participants will not be identified by name in the study database or on any study documents to be collected by the Sponsor (or designee), but will be identified by a participant study ID number.

*For eCRFs:* If a correction is required for an eCRF, the time and date stamps track the person entering or updating eCRF data and creates an electronic audit trail. *For paper CRFs:* If a correction is made on a CRF, the study staff member will line through the incorrect data, write in the correct data and initial and date the change.

### 16.2 Data Management Responsibilities

The study staff are responsible for ensuring the accuracy, completeness, legibility, and timeliness of the data reported. All source documents should be completed in a neat, legible manner to ensure accurate interpretation of data. The investigators will maintain adequate case histories of study subjects, including accurate case report forms (CRFs), and source documentation.

The PI is responsible for all information collected on participants enrolled in this study. All data collected during the course of this study must be reviewed and verified for completeness and accuracy by the PI, Co-I, or CRC. A copy of the CRF will remain at the PI's site at the completion of the study.

### 16.3 Database Protection

This study will use an electronic database and on-paper surveys and CRFs. The electronic database will be secured with password protection. The informatics manager will receive only coded information that is entered into the database under those identification numbers. Electronic communication with outside collaborators will involve only unidentifiable information. The database incorporates an electronic audit trail to show change(s) to data after original entry including the date/time and user making the change. For all paper-based study records will be kept in a locked filing cabinet. Code sheets linking a participant's name to the participant's study identification number will be stored separately in another locked filing cabinet or on a password-protected computer.

### 16.4 Source Document Protection

The study will be conducted according to the Declaration of Helsinki, Protection of Human Volunteers (21 CFR 50), Institutional Review Boards (21 CFR 56), and Obligations of Clinical Investigators (21 CFR 312).

To maintain confidentiality, all laboratory specimens, evaluation forms, reports and other records will be identified by a coded number and initials only. All study records will be kept

in a locked filing cabinet or on a password-protected computer or server. Code sheets linking a participant's name to a participant study identification number will be stored separately in another locked filing cabinet or on a password-protected computer.

All study data collected on an electronic CRF will be entered into a validated database. The database is safeguarded against unauthorized access by established security procedures. Throughout the study, device use data (i.e. frequency and duration of use, stimulation intensity used in a treatment session) and daily survey data will be upload by the smartphone's cellular data plan to a cloud-based, password-protected, secure server (Amazon Web Services). This data will also be stored securely on a password-protected server maintained by the sponsor at the sponsor's facility. Note that data files transmitted to and saved on the password-protected cloud server and the sponsor's server will be de-identified. These files will only include the participant's study ID number and Empower controller MAC address.

All procedures for the handling and analysis of data will be conducted using good computing practices meeting FDA guidelines for the handling and analysis of data for clinical trials.

